### **6.3.3. Migraine-Specific Quality of Life**

#### **6.3.3.1. Definition**

The MSQoL version 2.1 ([Appendix D](#)) is a 14-item questionnaire that assesses the impact of migraine and migraine treatment on a patient’s quality of life during the previous 4 weeks, which has been shown to be a reliable and valid tool for use in CM and EM. The MSQoL measures the degree to which performance of normal activities is limited by migraine (Role Function-Restrictive domain comprising 7 items), the degree to which performance of normal activities is prevented by migraine (Role Function-Preventive domain comprising 4 items), and the emotional effects of migraine (Emotional Function domain comprising 3 items). Scores range from 0 to 100, with higher scores indicating better health-related quality of life. [Appendix E](#) provides the scoring instructions on how to rescale the raw score to the scales that will be used for the analysis.

#### **6.3.3.2. Analysis**

The MSQOL domains (Role Function-Restrictive, Role Function-Preventive, and Emotional Function) scores change from baseline to week 12 will be analyzed using the same MMRM method as described in section [6.2.3.1](#). The analysis will also be done at weeks 4 and 8.

### **6.3.4. Clinical Global Impression-Severity Scale**

#### **6.3.4.1. Definition**

The CGI-S ([Appendix F](#)) is a short questionnaire filled out by the investigator that rates a patient’s mental health from 1 (normal, not at all ill) to 7 (among the most extremely ill patients).

#### **6.3.4.2. Analysis**

The CGI-S rating change from baseline to weeks 4, 8, and 12 will be analyzed using the same MMRM method as described in section [6.2.3.1](#).

### **6.3.5. 6-Item Headache Impact Test**

#### **6.3.5.1. Definition**

Migraine related disability will be assessed using the HIT-6 ([Appendix G](#)). The questionnaire measures the adverse impact of headache on social functioning, role functioning, vitality, cognitive functioning, and psychological distress. It also assesses headache severity. Each question is answered on the scale ranging with the following response options: 6 points (never), 8 points (rarely), 10 points (sometimes), 11 points (very often), and 13 points (always). The total

score is obtained from summation of the 6 question points. The HIT-6 total score ranges between 36 and 78, with larger scores reflecting greater impact.

#### **6.3.5.2. Analysis**

The HIT-6 disability score change from baseline to week 12 will be analyzed using the same MMRM method as described in section 6.2.3.1. The analysis will also be done at weeks 4 and 8.

### **6.4. Other Efficacy Endpoints Analysis**

The exploratory efficacy endpoints are listed in section 1.2.

#### **6.4.1. Patient Health Questionnaire-9**

##### **6.4.1.1. Definition**

The PHQ ([Appendix H](#)) is a 9-item questionnaire with each item corresponding to 1 criterion of the Diagnostic and Statistical Manual for Mental Disorders 4th edition diagnostic criteria for MDD. Each of the items is scored on a scale of 0 (“not at all”), 1 (“several days”), 2 (“more than half the days”), and 3 (“nearly every day”) based on the frequency of symptoms during the past 2 weeks. The PHQ-9 is a validated measure for detecting and monitoring depression, anxiety, and somatization.

##### **6.4.1.2. Analysis**

The PHQ-9 total score change from baseline to weeks 4, 8, and 12 will be analyzed using the same MMRM method as described in section 6.2.3.1, except that the baseline value will not be included in the model.

#### **6.4.2. Hamilton Anxiety Scale**

##### **6.4.2.1. Definition**

The HAM-A Scale ([Appendix I](#)) is a 14-item scale that measuring the severity of a patient’s anxiety. Each item is scored on a scale of 0 (not present) to 4 (severe), with a total score range of 0–56, where <17 indicates mild severity, 18–24 mild to moderate severity and 25–30 moderate to severe.

##### **6.4.2.2. Analysis**

The HAM-A total score change from baseline to weeks 4, 8, and 12 will be analyzed using the same MMRM method as described in section 6.2.3.1.

#### **6.4.3. Work Productivity and Activity Impairment Questionnaire General Health V2.0**

##### **6.4.3.1. Definition**

The generic version of the WPAI questionnaire ([Appendix J](#)) measures the overall effect of health on productivity at work and daily activities. The specific health problems version of the WPAI questionnaire allows investigators to attribute productivity and activity impairment issues to specific health conditions. After the employment status of a respondent is identified, 3 open

Statistical Analysis Plan

ended questions are asked concerning (1) hours absent from work due to health problems (or specific condition), (2) hours absent from work due to other reasons, and (3) hours actually worked. Two additional questions are included that ask about the impact of health on productivity, 1 concerning productivity at work and the other concerning daily activities outside of work. The response format of each item of the WPAI questionnaire consists of an 11-point scale ranging from 0 (no impairment) to 10 (complete impairment).

The following scores will be derived based on the WPAI:GH questionnaire. Multiply scores by 100 to express in percentages.

- percent work item missed due to health:  $\frac{Q2}{Q2+Q4}$
- percent impairment while working due to health:  $\frac{Q5}{10}$
- percent overall work impairment due to health:  $\frac{Q2}{Q2+Q4} + \left[ \left( 1 - \frac{Q2}{Q2+Q4} \right) \times \frac{Q5}{10} \right]$
- percent activity impairment due to health:  $\frac{Q6}{10}$

**6.4.3.2. Analysis**

For the patients who are currently employed, their scores of

- percent work item missed due to health
- percent impairment while working due to health
- percent overall work impairment due to health
- percent activity impairment due to health

change from baseline to week 12 will be analyzed using the same MMRM method as described in section 6.2.3.1. The analysis will also be done at weeks 4 and 8.

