### **5.3. Demographics and Baseline Characteristics**

The continuous variables of patient age, weight, height, and body mass index (BMI), and time since initial migraine diagnosis (years) will be summarized using descriptive statistics. The categorical variables of patient sex, race, ethnicity, migraine classification, country, region, PHQ-9 score category, patient sex as randomized, migraine classification as randomized, and PHQ-9 score category as randomized will be summarized using descriptive statistics for each category. Missing categories will be presented if necessary.

This summary will also be done for the open-label safety analysis set.

The baseline total number of migraine days, HAM-D 17 total score, MSQOL domain scores, CGI-S rating, HIT-6 disability score, PHQ-9 total score, HAM-A total score, and WPAI domain scores will be summarized using descriptive statistics.

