The **percentage of reduction** in the monthly average number of an efficacy variable will be calculated as

$$\frac{\text{baseline value} - \text{postbaseline value}}{\text{baseline value}} \times 100\% \quad (4)$$

where the baseline value is calculated by formula (3) and the postbaseline value in the equation is calculated by formula (1) for the variables *during the 12-week period* or by formula (2) for the variables *during the 4-week period* after each dose for months 1, 2, 3, and 6.

The mITT analysis sets will be used for all efficacy analyses. Summaries will be presented by treatment group as randomized, unless otherwise noted. For the double-blind treatment period, summaries will be presented by treatment group. For the open-label treatment period, summaries will be presented by double-blind treatment group and all patients (ie, total). Descriptive statistics for all efficacy data will be presented by month (or week), and over 12-week period for the double-blind period, and at month 6 (or week 24) for the open-label treatment period. For migraine days and PHQ-9 total score, months 1, 2, and 3 (or weeks 4, 8, and 12) will also be included in the open-label treatment period summaries.

The primary and secondary endpoints analysis listed in section 6.2.1 and section 6.3 will be repeated for the PP analysis set.

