The following questions ask about the effect of your health problems on your ability to work and perform regular activities. By health problems we mean any physical or emotional problem or symptom. *Please fill in the blanks or circle a number, as indicated.*

1. Are you currently employed (working for pay)? \_\_\_\_\_ NO \_\_\_\_\_ YES

*If NO, check “NO” and skip to question 6.*

The next questions are about the **past seven days**, not including today.

2. During the past seven days, how many hours did you miss from work because of your health problems? *Include hours you missed on sick days, times you went in late, left early, etc., because of your health problems. Do not include time you missed to participate in this study.*

\_\_\_\_\_ HOURS

3. During the past seven days, how many hours did you miss from work because of any other reason, such as vacation, holidays, time off to participate in this study?

\_\_\_\_\_ HOURS

4. During the past seven days, how many hours did you actually work?

\_\_\_\_\_ HOURS *(If “0”, skip to question 6.)*

Statistical Analysis Plan

5. During the past seven days, how much did your health problems affect your productivity while you were working?

*Think about days you were limited in the amount or kind of work you could do, days you accomplished less than you would like, or days you could not do your work as carefully as usual. If health problems affected your work only a little, choose a low number. Choose a high number if health problems affected your work a great deal.*

Consider only how much health problems affected productivity while you were working.

Health problems had no effect on my work	_____	Health problems completely prevented me from working
	0 1 2 3 4 5 6 7 8 9 10	

CIRCLE A NUMBER

6. During the past seven days, how much did your health problems affect your ability to do your regular daily activities, other than work at a job?

*By regular activities, we mean the usual activities you do, such as work around the house, shopping, childcare, exercising, studying, etc. Think about times you were limited in the amount or kind of activities you could do and times you accomplished less than you would like. If health problems affected your activities only a little, choose a low number. Choose a high number if health problems affected your activities a great deal.*

Consider only how much health problems affected your ability to do your regular daily activities, other than work at a job.

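### The exploratory WPAI activity-impairment score is modelled in employed patients only, although its single item is asked of everyone; a smaller point is that the PHQ-9 model drops the baseline score

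*SAP*

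**What the plan says.** **WPAI.** SAP 6.4.3.2 begins "For the patients who are currently employed, their scores of". Four bulleted scores follow, the last being activity impairment. Change from baseline to week 12, and also to weeks 4 and 8, goes into the MMRM of SAP 6.2.3.1.

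SAP 6.4.3.1 describes the two impact questions as one on productivity at work and "the other concerning daily activities outside of work". It defines activity impairment as Q6/10. The other three scores use Q2, Q4 or Q5.

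In SAP Appendix J, a patient who answers NO to the employment question is told to check that box "and skip to question 6". Question 6 asks how far health problems affected "your ability to do your regular daily activities, other than work at a job".

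Two other sections carry no employment limit. SAP 6.1 takes the mITT sets for all efficacy analyses and adds "Descriptive statistics for all efficacy data will be presented by month". SAP 5.3 covers baseline: "HAM-A total score, and WPAI domain scores will be summarized using descriptive statistics".

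On status, SAP 6.4 states "The exploratory efficacy endpoints are listed in section 1.2"; that list is not in the public text.

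**PHQ-9.** SAP 6.4.1.2 uses the same MMRM, "except that the baseline value will not be included in the model". The parent model in SAP 6.2.3.1 has both the baseline value and the as-randomized PHQ-9 category. The HAM-A analysis in SAP 6.4.2.2 uses that model without any exception.

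**The concern.** For the three work scores the restriction is unavoidable, because they cannot be computed without work data. For activity impairment it is not needed: the item contains nothing about paid work, and the form is built to collect it from patients without a job. The restriction departs from the mITT default for this one score, and the visible text gives no reason.

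Two things follow. The modelled treatment effect on daily activities describes employed patients only, although the trial population is defined by migraine and MDD. It also usually rests on fewer data than were collected.

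The PHQ-9 exception is a matter of precision. A baseline score that has already been collected is left out of a model for change in that same score.

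**Working it through.** **The plan's own figures.** The documents give no power or precision figure for WPAI or PHQ-9. The sample size used below as denominator reproduces. With power = Φ(δ/(σ√(2/n)) − 1.96) and n = 144 per group:

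- migraine days, δ = 2, σ = 5.2: 0.904 (stated 90%)
- HAM-D 17, δ = 2, σ = 6: 0.807 (stated about 80%)
- dropout: 144/0.85 = 169.4, so 170 per group and 340 in total (stated about 340)

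**What each WPAI score needs.**

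| Score | Items used | Answered by patients without a job? |
|---|---|---|
| Work time missed | Q2, Q4 | No |
| Impairment while working | Q5 | No |
| Overall work impairment | Q2, Q4, Q5 | No |
| Activity impairment | Q6 | Yes |

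**Precision lost on Q6.** This is a two-group approximation without covariates. Let p be the employed share and k the SD in patients without a job divided by the SD in employed patients. Both are assumptions.

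- Patients left out = 288(1 − p)
- SE(employed only)/SE(all) = 1/√(p(p + (1 − p)k²))

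| p | Left out of 288 | k = 1.0 | k = 1.2 | k = 1.5 |
|---|---|---|---|---|
| 0.80 | 58 | 1.118 | 1.072 | 1.000 |
| 0.65 | 101 | 1.240 | 1.155 | 1.035 |
| 0.50 | 144 | 1.414 | 1.280 | 1.109 |

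In terms of power, with k = 1, take an effect that has 80% power in all 288. Restricted power is Φ((1.96 + 0.842)√p − 1.96), which gives 71%, 62% and 51% for the three shares.

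**Shift in what is estimated.** Let h be the effect in patients without a job divided by the effect in employed patients (assumption). The employed-only effect relative to the all-patient effect, minus 1, is 1/(p + (1 − p)h) − 1.

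- h = 0.5: +11%, +21%, +33% for p = 0.80, 0.65, 0.50
- h = 1.5: −9%, −15%, −20%

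If h = 1 there is no shift.

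**PHQ-9.** The category (10–14, 15–19, 20 or more) stays in the model, so the loss is the baseline information within categories, assuming the as-randomized category is correct. Let W be the within-category variance of the baseline score.

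- Uniform on 10–27: 10 of 18 values lie in categories with variance 2 and 8 of 18 in one with variance 5.25, so W = (10 × 2 + 8 × 5.25)/18 = 3.44. The category explains 87% of the total variance.
- Discretized normal(15, 4) truncated to 10–27: W = 1.96. The category explains 83%.

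With b points of change per baseline point and residual SD s, adding the score lowers the SE by 1 − √(s²/(s² + b²W)). The equivalent in patients is 288 × (1 − s²/(s² + b²W)).

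| Baseline distribution | b = 0.3, s = 6 | b = 0.7, s = 5 |
|---|---|---|
| Truncated normal | 0.24%, 1.4 patients | 1.87%, 10.7 patients |
| Uniform | 0.43%, 2.5 patients | 3.21%, 18.2 patients |

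More pessimistic inputs (b = 0.5 to 1, s = 4 to 6, even spread within category) make the SE without the score about 1% to 6% larger in the two lower categories and 2% to 15% larger in the top one.

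**The case against.** The reading of the text is not in dispute. The case against concerns weight and detail.

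- **It is an open choice, and its reason may be out of sight.** The exploratory endpoint list is not visible and the matching protocol sections are redacted, so the endpoint may have been defined for employed patients. One common population for all four scores is also defensible. This stands: the point is an analysis choice, not a contradiction.
- **The data are not lost.** The descriptive summaries have no employment limit. This stands, but they do not replace the adjusted comparison.
- **The size rests on assumptions.** This also stands: the precision loss runs from nothing to 41%. The effect-ratio figures describe a different target population, not an error in the employed-patient estimate.
- **The denominator is planned completers.** The mITT set could approach 340, and the numbers left out would then be 68, 119 and 170. The SE ratios do not change.
- **Employment timing is undefined.** The form is completed at visits 2 to 6, and the SAP does not say which answer defines current employment. Read visit by visit, the restriction conditions on a post-randomization status. Modelling Q6 in all patients removes this for Q6; it remains for the work scores.
- **The PHQ-9 exception may be deliberate.** PHQ-9 is scheduled at visit 1 but not at visit 2, so score and category normally come from one measurement. The gain is small. Nor is freedom from bias absolute: it holds for the randomized comparison with complete data, but if dropout depends on baseline severity within category, leaving the score out could matter slightly.

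**Conclusion.** The concern holds as a minor improvement. As written, SAP 6.4.3.2 excludes from the only modelled comparison of activity impairment patients whose answers are collected and usable, for no visible reason. For employed shares of 80% to 50% and equal SD and effect, the standard error is 12% to 41% larger than it need be. With an SD 1.5 times as large in patients without a job, the excess falls to between 0% and 11%. The result also applies to employed patients only, which matters if the effect differs by employment.

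The PHQ-9 omission costs about 0.2% to 3.2% of the standard error under the main assumptions and more under harsher ones. It introduces no bias into the randomized comparison with complete data.

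The employed share, SD ratio, effect ratio, slope and residual SD are all assumptions. Both analyses are exploratory, and no primary or secondary conclusion depends on them.

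**What to change.** **SAP 6.4.3.2.** Keep the three work scores in currently employed patients. Analyse activity impairment with the same MMRM in all double-blind mITT patients with Q6 data, whatever their employment. The employed-only activity result can be shown beside it. It would help to state in the same edit which visit's answer defines employment for the work scores.

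**SAP 6.4.1.2.** Delete the exception, so that the baseline PHQ-9 total score enters as a covariate and the as-randomized category stays.

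**Cost.** Two wording edits, with no new data, visits or patients. If the SAP is already final, run both as labelled supplementary analyses.

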**6.4.4. Other Analysis**

Correlation between the change from baseline in the PHQ-9 total score and the change from baseline in the monthly average number of migraine days will be presented with all visits combined through the 24-week period after the first dose of study drug. All visits will be combined and both treatments will be combined in the analysis. The open-label mITT analysis set will be used for the analysis. A scatter plot will also be presented.

To assess whether improvements in headaches precede changes in depression, a graph of mean change from baseline in monthly number of migraine days versus mean change from baseline in PHQ-9 total score during the 6-month treatment period will be presented by month and double-blind treatment group. The open-label mITT analysis set will be used for the graph.

